4.3.2 Data Monitoring Committee

An independent Data Monitoring Committee (DMC) will be formed to monitor the ongoing safety of the study through periodic review. The general scope of DMC activities is presented in the protocol, and the composition and operation of the DMC will be defined in the DMC charter. The presentation and analysis of data for the DMC meetings will be described within a separate DMC SAP.

4.4 Multicenter studies

The data from all centers will be pooled for the purposes of the analysis. However, the effect of center (using a pooling of centers by region) on results will be evaluated as mentioned in [Section 3.8](#).

4.5 Multiple comparisons/multiplicity

A fixed sequence testing procedure will be applied for the primary endpoint and the key secondary endpoints. The testing procedure will account for multiplicity and control the family-wise type I error rate at $\alpha=0.05$ (2-sided).

For each test, on each binary efficacy endpoint, the null hypothesis is that the conditional odds ratio is equal to one ($H_0: OR_{T1T2} = 1$). The alternative hypothesis is that the conditional odds ratio is not equal to one ($H_A: OR_{T1T2} \neq 1$).

For each test, on each continuous efficacy endpoint, the null hypothesis is that there is no difference between treatment groups ($H_0: T_1 - T_2 = 0$). The alternative hypothesis is that there is a difference between treatment groups ($H_A: T_1 - T_2 \neq 0$).

T_1 refers to BKZ and T_2 to placebo.

According to this strategy, the statistical testing of an endpoint can be investigated only if the null hypothesis for the previous endpoint has been rejected (ie, if $p < 0.05$). [Table 7-4](#) shows the testing order for these endpoints.

Table 7-4: Sequential testing procedure of primary/secondary efficacy endpoints (fixed testing procedure procedure) (All efficacy endpoints at Week 16)

BKZ 160mg Q4W	
H ₁	ACR50 Response superior to Placebo
H ₂	Change from Baseline HAQ-DI superior to Placebo

H ₃	PASI90 Response superior to Placebo in subjects with PSO BSA $\geq 3\%$ at Baseline
H ₄	Change from Baseline SF-36 PCS superior to Placebo
H ₅	MDA superior to Placebo

ACR50=American College of Rheumatology 50% response criteria; BKZ=bimekizumab; H=hypothesis; HAQ-DI=Health Assessment Questionnaire - Disability Index; MDA=Minimal Disease Activity; PASI90=Psoriasis Area and Severity Index 90; PCS=Physical Component Summary; Q4W=every 4 weeks; SF-36=Short-Form 36-item Health Survey; W=week.

4.6 Use of an efficacy subset of subjects

The RS will be the primary analysis set for efficacy analyses, but analyses will also be repeated on the FAS and the PPS for the primary efficacy endpoint. The FAS analysis will evaluate whether there are differences in the efficacy analysis between randomized subjects and randomized subjects with a Baseline assessment; while the PPS analysis will evaluate the effect of IPD on the analysis.

4.7 Active-control studies intended to show equivalence

Efficacy outcomes are based on superiority comparisons of the BKZ 160mg sc Q4W to placebo, this section is then not applicable for this study.

4.8 Examination of subgroups

Subgroup analyses will be performed on the variables below. They are all assessed at Baseline, except concomitant cDMARDs, concomitant Methotrexate (MTX) and ADAb status which will be assessed during the 16-week period. Subgroup analyses will be performed on the ACR50 response, the PASI90 response and the HAQ-DI response (subjects with a decrease of HAQ-DI from Baseline of at least 0.35) at Week 16. The ADAb status will also be used for subgroup analysis for the PK endpoints.

The variables for subgroup analyses will be:

- Age (<45 years of age, ≥ 45 years of age),
- Gender (male, female),
- Disease duration (<1 year, ≥ 1 year),
- Region (eg, North America, Western Europe, Eastern Europe, Asia. Western Europe will be combined with Asia if any of these 2 regions have less than 10% of the randomized subjects),
- Race (White, Black, and Other),
- Body weight at Baseline (≤ 100 kg, > 100 kg),
- Prior TNF α exposure (intolerance to TNF α inhibitor, inadequate response to at least 1 TNF α inhibitor, inadequate response to 2 prior or more TNF α inhibitors),
- hs-CRP at Baseline (<6mg/L, ≥ 6 mg/L),
- Prior conventional disease-modifying antirheumatic drugs (cDMARDs) (0, 1, ≥ 2) (taken prior to Baseline). Such medications will be classified using an adjudicated spreadsheet.
- Concomitantly receiving cDMARDs versus no concomitant cDMARDs,
- Concomitantly receiving MTX versus no concomitant MTX,

- Concomitantly receiving MTX at Baseline vs. other cDMARDs at Baseline (MTX at Baseline, no MTX at Baseline and cDMARDs at Baseline, no MTX at Baseline and no cDMARDs at Baseline),
- PSO affected BSA at Baseline (<3%, ≥3% to 10%, >10%),
- BASDAI at Baseline (<4, ≥4),
- ADAb status (positive, negative) (See [Section 9.2](#)) for the BKZ 160mg Q4W group only,
- Human leukocyte antigen B27 (HLA-B27) (positive, negative).

Note: In the context of submission for Japanese health authorities, a subset of tables, listings and figures will be provided for the subgroup of subjects randomized in Japan.

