6.2.2 Other baseline characteristics

The following variables will be summarized by treatment group and overall:

- Prior TNF α exposure (Intolerance to TNF α inhibitor, Inadequate response to 1 TNF α inhibitor, Inadequate response to 2 TNF α inhibitors) – IXRS randomization strata
- Prior TNF α exposure (Intolerance to TNF α inhibitor, Inadequate response to at least 1 TNF α inhibitor, Inadequate response to 2 prior or more TNF α inhibitors) – actual randomization strata
- % of BSA affected by PSO ($< 3\%$, $\geq 3\%$ to $\leq 10\%$, $> 10\%$)
- PASI score at Baseline (for subjects with PSO involving at least 3% of BSA at Baseline). This variable will be summarized as a continuous variable and in classes (< 10 , 10 to 20, > 20)
- BASDAI (< 4 , ≥ 4)
- Rheumatoid factor (positive, negative). A rheumatoid factor value < 30 IU/mL is defined as negative and a value ≥ 30 IU/mL is defined as positive. (Chemistry results / Proteins / Test=RF).
- Anti-cyclic citrullinated peptide (CCP) antibodies (Positive, Negative). Anti-CCP antibodies negative is a value < 20 U/mL and a value ≥ 20 U/mL is defined as positive.
- Nail psoriasis (yes, no)
- Dactylitis (“yes” if LDI score > 0 , “no” if LDI score = 0 or missing)
- Enthesitis based on LEI (“yes” if LEI score > 0 , “no” if LEI score = 0 or missing)
- Enthesitis based on SPARCC (“yes” if SPARCC > 0 , “no” if SPARCC = 0 or missing)
- Prior NSAID (yes, no)
- NSAID at Baseline (yes, no)
- Past cDMARDs therapy (yes, no)

- Prior cDMARDs (0, 1, ≥2) (see [Section 4.8](#))
- cDMARDs at Baseline (yes, no)
- HLA-B27 status (positive, negative)
- Methotrexate at Baseline (yes, no)
- Prior oral corticosteroids (yes, no)
- Oral corticosteroids at Baseline (yes, no)

The above data including extra-articular assessments will also be listed.

Efficacy variables not listed above will not be presented in the Baseline characteristics section. They will be presented in by-visit tables in the context of the analysis of secondary and other efficacy variables.

To understand the study population during the different periods of the COVID-19 pandemic, the reporting of Baseline demographics will be repeated by COVID-19 period (pre-, during, and post- as determined by the Baseline visit date) on the SS.

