6.4 Prior and concomitant medications

Prior medications include any medications that started prior to the start date of the first IMP administration.

Concomitant medications are medications taken at least one day in common with the study medication dosing period.

The IMP dosing period corresponding to the combined Double-Blind Treatment Period will be calculated as follows:

- The study medication dosing period start date is defined as the date of first dose.

The study medication dosing period stop date is defined as follows:

- For subjects who are ongoing at the time of the clinical data cut (not including subjects who are in SFU) use date of last clinical contact
- For subjects who died prior to last visit (not including those who died during SFU), use the minimum of the following:
 - Date of death
 - Date of last dose of any study medication + 28 days
- For subjects who complete the study as planned, the dosing period ends at the later of the following two dates:
 - Date of last administration of IMP + 28 days
 - The last scheduled visit date not including SFU
- For all other subjects, use the maximum of the following:
 - Date of last dose of any study medication + 28 days
 - Date of last visit (not including SFU)

In the case of missing data, the classification of medications as prior or concomitant will be performed as described in [Section 4.2.4](#). Imputations of missing data will be performed before calculation of relative study days.

The number and percentage of subjects taking prior medications and prior Anti-TNFs (excluding past psoriasis medications) will be summarized on the SS by treatment group, overall and by ATC class, presenting Anatomical Main Group (ATC Level 1), Therapeutical/Pharmacological Subgroup (ATC level 3), and preferred term (PT).

The table summary will be ordered alphabetically for the ATC class and in terms of decreasing frequency for PT within ATC class in the BKZ treatment group. In the event of ties, PT will be ordered alphabetically.

A by-subject listing of all prior medications and prior Anti-TNFs and concomitant medications on the SS as well as glossary of all medical medications will be provided.

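### The concomitant-cDMARD and concomitant-MTX subgroups are set by use during treatment, so treatment can affect membership for subjects who start after randomization; the bias is probably small and the fix is free

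*SAP*

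**What the plan says.** SAP Section 4.8 lists the subgroup variables for ACR50, PASI90 and HAQ-DI response at Week 16 and gives a timing rule: "They are all assessed at Baseline, except concomitant cDMARDs, concomitant Methotrexate (MTX") and "ADAb status which will be assessed during the 16-week period". The two medication rows read "Concomitantly receiving cDMARDs versus no concomitant cDMARDs" and "Concomitantly receiving MTX versus no concomitant MTX". ADAb status, the third exception, is restricted to the BKZ group and so gives no comparison between arms. The medication rows have no such restriction.

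Section 4.8 does not define 'concomitant'. The only definition in the SAP is in Section 6.4: "Concomitant medications are medications taken at least one day in common with the study medication dosing period". It does not require use at Baseline. Section 6.4 also fixes when the dosing period ends. For subjects who do not fall under its special cases the rule is "For all other subjects, use the maximum of the following": last dose plus 28 days, or last visit before safety follow-up.

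Section 8.1.3 fits a logistic model on the Randomized Set with a subgroup term and a subgroup-by-treatment interaction. It reports response rates, odds ratios and rate differences per category, and puts the odds ratios with their intervals on a forest plot. Sections 8.2.3 and 8.3.1.25 apply the same method to PASI90 and HAQ-DI response.

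Baseline versions exist. Section 6.2.2 lists "cDMARDs at Baseline (yes, no") and "Methotrexate at Baseline (yes, no"). The next row in Section 4.8, a three-level MTX/other-cDMARD subgroup, is defined entirely at Baseline.

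**The concern.** A subgroup comparison keeps the benefit of randomization only if membership is settled before treatment can act. Here a subject with no cDMARD at first dose who starts one during the 16 weeks counts as a concomitant user. If the start is prompted by poor response, non-responders leave the 'no concomitant' group and enter the 'concomitant' group. If that happens more often on one arm, the two odds ratios separate although the true effect is the same in both.

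The SAP's own rules leave room for a link with outcome. Subjects who stop IMP are encouraged to keep attending through Week 16 (Section 2.3.1), and the Section 6.4 window can run to their last visit. A drug started after stopping IMP can then count as concomitant, while the same subject is a non-responder by imputation (Section 4.2.2.1).

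What is at stake is the reading of two rows in each of three exploratory subgroup tables, on whether benefit differs with and without background therapy.

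**Working it through.** **Inputs from the SAP (Section 2.4.1).** ACR50 26% on BKZ and 10% on placebo; 260 and 130 subjects; two-sided 0.05.

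**The plan's own figure.** OR = (0.26/0.74)/(0.10/0.90) = 3.16, as stated. Power by the continuity-corrected formula is 96.6%, against 96% stated. The rates are therefore a fair anchor.

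**Assumptions, not in the SAP.**
- The true OR is 3.16 in both subgroups.
- A share b of 40-60% uses a cDMARD at Baseline.
- Only non-responders without Baseline use start one: a share s on placebo and s/4 on BKZ.

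**Formulas.** For an arm with response rate p and start share s:
- 'No concomitant': responders (1-b)p, non-responders (1-b)(1-p)(1-s), so the odds are p/[(1-p)(1-s)].
- 'Concomitant': responders bp, non-responders (1-p)[b+(1-b)s], so the odds are bp/{(1-p)[b+(1-b)s]}.

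Hence, with P for placebo and B for BKZ:
- OR('no concomitant') = 3.16 × (1-s_P)/(1-s_B), whatever b is.
- OR('concomitant') = 3.16 × [b+(1-b)s_P]/[b+(1-b)s_B].

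| s placebo | s BKZ | OR 'no concomitant' | OR 'concomitant' (b = 0.6 to 0.4) |
|---|---|---|---|
| 2% | 0.5% | 3.11 | 3.19 to 3.23 |
| 5% | 1.25% | 3.04 | 3.24 to 3.34 |
| 10% | 2.5% | 2.92 | 3.32 to 3.51 |

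Example, last row with b = 0.4: 3.16 × 0.90/0.975 = 2.92, and 3.16 × 0.46/0.415 = 3.51.

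**Equal start shares.** Both correction factors equal 1, so both ORs stay at 3.16. The response rates still move. Placebo 'no concomitant' becomes 0.10/[0.10 + 0.90(1-s)], which is 10.2% at s = 2% and 11.0% at s = 10%, instead of 10%.

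**Against the noise.** With half the subjects in each subgroup (130 BKZ, 65 placebo), the SE of a log OR is √(1/33.8 + 1/96.2 + 1/6.5 + 1/58.5) = 0.46. The 95% interval around 3.16 is then roughly 1.3 to 7.8. At s = 10% and b = 0.5 the ORs are 2.92 and 3.39, and ln(3.39/2.92) = 0.15. The SE of that difference is about 0.46 × √2 = 0.65, so the artefact is about a quarter of one SE.

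**Who moves.** A subject taking the drug at first dose has one day of overlap and stays in the 'concomitant' group even if the drug is stopped the next week. Only starters after first dose change group.

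**The case against.** The strongest case against runs as follows. The timing is stated openly. The mechanism needs subjects to start a cDMARD or MTX within 16 weeks, and at different rates by arm. The SAP shows neither: Section 2.3.2 has Screening verify that permitted DMARD doses are stable, and Section 6.5 leaves prohibited and restricted medication to the protocol. If few subjects start, the two definitions nearly coincide. The analyses lie outside the testing hierarchy of Section 4.5, and the Baseline-defined three-level subgroup appears in the same list, so a clean answer to the background-therapy question is already planned.

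All of that stands, and it limits the weight of the point. It does not make during-treatment membership a sound basis for comparing arms, and the SAP gives no reason for treating these two rows differently from the neighbouring one.

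Two stronger readings are tempting and are not supported. A reader might infer that a subject who stops MTX for an adverse event changes group; the one-day rule in Section 6.4 rules this out for anyone on MTX at first dose. A reader might also infer that biased interactions will be displayed on the forest plot. Section 8.1.3 fits an interaction term, but the plot carries only odds ratios and intervals, and no interaction estimate or p-value is listed as output.

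**Conclusion.** The point holds as a minor one. In the concomitant-cDMARD and concomitant-MTX subgroups, subjects who start after randomization are classified by something that treatment and response can influence, so the rates and odds ratios in those two subgroups are not randomized comparisons. On the assumed start rates, a common OR of 3.16 becomes about 2.9-3.1 without and 3.2-3.5 with concomitant use. That is well inside the sampling error of either subgroup. With equal start shares the ORs do not move and only the response rates do.

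The size rests on assumed start rates, a 4:1 placebo-to-BKZ ratio of start shares, and 40-60% Baseline use; the SAP gives none of these. A smaller Baseline share, as may apply to MTX alone, would enlarge the shift in the 'concomitant' group. It also rests on Section 6.4 supplying the meaning of 'concomitant' in Section 4.8. The primary analysis, the hierarchy, the sample size and the power are unaffected.

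**What to change.** In Section 4.8, define both subgroups by use at Baseline, with the existing flags of Section 6.2.2 (cDMARDs at Baseline, Methotrexate at Baseline), and state that this means in use at first dose. Remove the two variables from the list of exceptions to the Baseline rule, leaving only ADAb status. This aligns them with the three-level MTX/other-cDMARD subgroup. If use during treatment is of interest, tabulate it by arm as a description, without odds ratios or rate differences between BKZ and placebo.

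The cost is a change of SAP wording and of the variable named in the subgroup programs. It needs no new data and leaves the sample size as it is.

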5 STUDY POPULATION CHARACTERISTICS

5.1 Subject disposition

Subject disposition will be summarized for all subjects screened overall, by region and by site. In this summary, the dates of first subject screened and date of last subject last visit (end of study), number of screened subjects, and the number of subjects included in each analysis set (RS, SS, FAS, PPS, PK-PPS, COVID-19-free Set) will be presented.

The disposition of subjects into treatments groups and analysis sets will also be summarized on the RS.

Reasons for screen failures (as collected on the Study Termination Screen Failure CRF page) will be summarized for all screened subjects who failed to be randomized.

The number and percentage of randomized subjects who completed the study, completed the study not on randomized treatment, who discontinued IMP, overall and by reason, and who discontinued the study, with the primary reason for study discontinuation (as collected on the Study Termination CRF page), will be tabulated overall and by treatment group. The numbers and percentage of randomized subjects entering the SFU Period will additionally be presented. The numbers and percentages of these subjects who either complete the SFU visit or not will additionally be presented. The numbers and percentages of randomized subjects entering the Open Label Extension (OLE) study and those not entering the OLE study will also be presented.

A subject will be said to have completed the study if she/he had completed the last scheduled study visit, not including SFU visits. (The SFU visit is typically 140 days post last dose of IMP, which is roughly equivalent to 5 half-lives of BKZ). For subjects who previously discontinued IMP, the primary reason for discontinuation as collected on the Study Medication termination CRF page will be summarized in a separate table.

Finally, the number of randomized subjects who discontinued the study due to AEs by type of AEs (serious fatal, non-fatal, other) will be summarized.

Study disposition and termination details will be listed for all subject screened. Additional listings will be created on study discontinuation, subject analysis sets and visit dates (both actual visit and visit remapped for analysis). A listing will also be provided for subjects who did not meet the study eligibility criteria.

To assess subject disposition (entry and periods in the study) during the COVID-19 pandemic, subject disposition will be assessed by period of the COVID-19 pandemic (pre – during – post) ([Section 3.6.7](#)), by comparing the dates of visits (or events) to the dates of the COVID-19 pandemic period.

5.2 Impact of COVID-19

A listing of visits affected by COVID-19 will be presented based on the ES including the visit, date of visit, relationship to COVID-19, impact category, and a narrative (short description) of the event. These data will be summarized for non-randomized subjects and by treatment group and overall, for enrolled subjects.

A summary of study visits by COVID-19 pandemic period (pre – during – post) will be presented for subjects enrolled prior, during and after the pandemic.

In addition, in order to assess the potential impact of COVID-19 on the collection and reporting of efficacy data, a separate summary on the RS will be presented to display missing data as well as data collected via an alternative modality (eg, phone, video call) for efficacy endpoints included in the hierarchy ([Table 7-4](#)). For these displays, missing data will be presented only for visits affected by COVID-19, as reported on the dedicated eCRF page. Missing data at other visits and for other reasons will not be included.

For visits conducted remotely, it was not possible to assess some endpoints (eg, TJC, SJC, LDI, LEI, PASI, etc.) and therefore these assessments will be missing for those visits. In addition, for any missed visit or visit conducted remotely, the CRP assessment will also be missing. Such assessments will be considered missing as a result of the COVID-19 pandemic. For these visits, it will therefore not be possible to assess composite endpoints like ACR response. For this summary table, based on the RS, only visits at which efficacy assessments are scheduled will be included.

5.3 Protocol deviations

The definition of an IPD is given in [Section 3.5](#).

A summary displaying the number and percentage of subjects with an important protocol deviation will be provided for the RS by treatment group. This will include a summary of subjects excluded from the PPS and PK-PPS. The summary will be provided overall and by type of deviation (inclusion criteria deviation, exclusion criteria deviation, withdrawal criteria deviation, prohibited concomitant medication, incorrect treatment or dose, treatment non-compliance, procedural non-compliance, COVID-19 related IPD) as well as the number and percentage of subjects excluded from the PPS due to reason other than PD. Criteria for exclusion of subjects from the PPS or PK-PPS will be defined in a separate document.

A listing of important protocol deviations will be provided for all subjects in the RS.

A listing of COVID-19 related PDs will be provided for all subjects in the RS.

A listing of subjects excluded from the PPS for reasons other than IPD will be provided.

6 DEMOGRAPHICS AND OTHER BASELINE CHARACTERISTICS

Unless otherwise specified, all summaries will be based on the SS and repeated using the RS (unless the SS and RS analysis sets are identical).

6.1 Demographics

The following demographic variables measured at Baseline will be summarized overall and by treatment group: age (years), gender, country, geographic region, country, race, ethnicity, height (cm), body weight (kg) and body mass index (BMI) (kg/m²).

Age, body weight and BMI will be summarized as continuous variables and as categorical variables based on the categories specified below.

For age, 3 sets of categories will be defined:

- ≤18, 19 to <65, ≥65 years (clinicaltrials.gov requirement),
- 18 to <65, 65 to <85, ≥85 years (EudraCT requirement),
- 18 to <45, ≥45 to <65, ≥65 years.

Body weight categories will be: ≤100, >100 kg.

Even if BMI is available in the database, BMI (in kg/m²) will be recalculated during analysis based on height (in m) and weight (in kg) values collected in the database, and the calculated values will be used in the statistical analysis since they are considered more accurate. The formula for BMI (kg/m²) calculation is:

$$\text{BMI} = \frac{\text{Weight (kg)}}{(\text{Height (m)})^2}$$

BMI categories will be: <25, 25 to <30, ≥30 to <35, ≥35 kg/m².

A separate frequency table will summarize the subject's lifestyle on the SS.

By-subject listings on demographics and female subjects' childbearing potential and birth control data will be provided for all screened subjects. Listing on lifestyle will be provided on the RS.

To understand the study population during the different periods of the COVID-19 pandemic, the reporting of Baseline demographics will be repeated by COVID-19 pandemic period (pre - during as determined by the Baseline visit date) on the SS.

